We will measure tremor and/or bradykinesia in persons with PD during DBS. Subjects will be familiarized with and able to practice the evaluation tasks before preparation for surgery. Further, they will be asked to discontinue use of dopaminergic and/or anti-tremor medications overnight prior to the study (as is the clinical routine for this procedure), to reduce variability of motor symptoms due to the time course of medications. We will conduct evaluations using unilateral stimulation, with the limb contralateral to the side of stimulation used for measurement of motor symptoms. Subjects may also be asked to rate any side effects that they experience on a 0 - 10 scale.

Contacts on the subject's DBS electrode will be used for stimulation and recording, with a second electrode in either STN or GPi/GPe used for recording. The four DBS contacts are designated as 0-1-2-3 in the ventral-dorsal direction. For monopolar stimulation, a single contact will be used for cathodic stimulation (1- or 2-) and a conductive pad will be placed on the subject's skin, outside of the sterile field, to serve as the return electrode. The recording contacts will be two other contacts on the DBS lead. For bipolar stimulation, DBS pulses will be applied between two electrode contacts, and the recording contacts will be the two remaining free contacts. The stimulus waveform will be a charge-balanced biphasic pulse, with charge restricted to values below the limit set by the manufacturer, 30 $\mu\text{C}/\text{cm}^2$. Another conductive pad will be placed on the subject to serve as the recording reference. The

DBS lead cannula or a surgical retractor normally placed at the cranial incision site may also be used as the recording reference or return electrode.

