For bradykinesia measurements, the subject will be instructed to press alternately the right and left buttons of a computer mouse with the index and middle finger of their hand as rapidly and regularly as possible. Bradykinesia will be measured as the timing of alternating finger presses, a validated test of bradykinesia [Taylor-Tavares et al., 2005].

Before DBS surgery, the subject's baseline pathological motor symptoms may be assessed in the pre-operative setting, to familiarize the patient with the task ahead of the implant procedure. Tremor or bradykinesia will be measured using the previously-described accelerometer measurement or the mouse click task, respectively. This task will take about 5 minutes, and will be performed in the DBS-off condition. No sedation will be administered until after this has been completed.

Following DBS surgery, the subject's pre-operative MRI and post-operative high-resolution CT scans may be used to determine the location of DBS electrode contacts within the brain. Placement of the electrode during DBS implant surgery will not be altered by the research study.

Study Interventions

The stimulation and recording system applies deep brain stimulation (DBS) and simultaneously measures the DBS local evoked potential (DLEP) and/or local field potential (LFP) responses from either the same or a second DBS electrode. Stimulation will be delivered through either an optically isolated stimulator (bp isolator, FHC Inc.) and pulses controlled by a high-speed digital-to-analog converter via MATLAB (Mathworks, Inc.), or the Medtronic RC+S test device. Both of these stimulation/recording devices are nonsterile and outside of the sterile field and will be connected to the DBS electrode using sterile connecting wires. The DBS lead cannula or a surgical retractor normally placed at the cranial incision site may be used as a return electrode. The locations used for the return electrode and recording reference will be recorded on the case report form.

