The data set will consist of recordings of neural and/or LFP recordings, and either mouse click timing data for measurement of bradykinesia in Parkinson's disease subjects or tremor accelerometry data for patients with Parkinson's disease. The DLEP recordings will be serially averaged with stimulus-triggering to remove random noise while preserving the evoked response. The signal-to-noise ratios of DLEP recordings will be compared across data sets to determine which combination of stimulation and recording sites maximize recording quality. We will quantify performance on the mouse click timing task by the delay between key presses and the time each key is held. Tremor will be quantified by calculating the total power within a window of the power spectrum of the time series of the tremor. We will perform ANOVA and post-hoc statistical analysis, in which the amplitude, frequency, and contact configuration used for stimulation will be the independent variables, and with dependent variables describing bradykinesia, tremor, and DLEP characteristics. We will also calculate correlation coefficients between tremor or bradykinesia and DLEP characteristics. Data and statistical analyses will be conducted by the study team, including the study statistician, [name] (Associate Professor of Biostatistics and Bioinformatics).

Additionally, clinical study staff may use pre- and post-operative brain imaging to determine the location of implanted DBS electrode contacts. The only data generated from this analysis will be a determination of the location of the contacts used to record neural activity (DLEPs and/or LFPs) relative to the brain region targeted for stimulation. Other study staff will analyze DLEP and/or LFP recordings obtained during surgery to generate a prediction of recording contact location prior to imaging analysis for each subject, and clinical study staff will be blinded to these predictions during imaging analysis.

Subjects will be included in data analysis if DBS is clinically effective at reducing motor symptoms for particular stimulation parameters, and DLEP and/or LFP data are observed during at least one trial.

[name] and [name] [name] conduct a total of 4-6 new DBS implants for PD per month. We have recruited approximately 1 subject per month at Duke over the past 18 months to participate in other intraoperative studies. Thus, we expect to recruit a maximum of 32 subjects during the course of this study at Duke University.

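### When bipolar stimulation and recording share a lead, the stimulating pair fixes the recording pair, so the ANOVA effect of contact configuration on the DLEP cannot be attributed to stimulation alone

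*Combined protocol and SAP*

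**What the plan says.** Study Design and Procedures describes the lead: "The four DBS contacts are designated as 0-1-2-3 in the ventral-dorsal direction". For bipolar stimulation it gives the rule "For bipolar stimulation, DBS pulses will be applied between two electrode contacts, and the recording contacts will be the two remaining free contacts". For monopolar stimulation the cathode is contact 1 or contact 2, and "The recording contacts will be two other contacts on the DBS lead", without saying which two. Recording from another lead is also allowed, "with a second electrode in either STN or GPi/GPe used for recording"; Study Interventions likewise refers to "responses from either the same or a second DBS electrode". Risk / Benefit Analysis says that only some patients receive two leads and gives no number.

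Contact configuration is varied from trial to trial within a subject, in randomized order. In Data Analysis and Statistical Considerations, "the amplitude, frequency, and contact configuration used for stimulation will be the independent variables", and DLEP characteristics are among the dependent variables. Correlations of DLEP characteristics with tremor or bradykinesia are also planned; the text does not say whether trials from different configurations are pooled. The same section compares signal-to-noise ratios by the combination of stimulation and recording sites, but does not carry that framing into the ANOVA or the correlation.

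On data capture, Study Interventions says: "The locations used for the return electrode and recording reference will be recorded on the case report form". It does not mention logging the recording pair.

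**The concern.** Background and Significance reads the size and form of the DLEP as showing which neuronal elements were activated and how widely. That reading needs a recording arrangement that stays put while stimulation changes. Here, in same-lead bipolar trials, moving the stimulating contacts necessarily moves the recording contacts. A DLEP difference between two configurations may then come from different activation, from a different view of the same activation, or from both. The ANOVA as worded credits all of it to stimulation. The same section of the protocol accepts that DLEP shape and magnitude may depend on electrode location, so the issue is not foreign to the plan.

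At stake is the interpretation of the configuration effect on the DLEP. If trials are pooled across configurations, the DLEP-symptom correlation is also exposed, since part of its scatter or association could come from changes of recording pair.

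**Working it through.** The plan gives no sample-size or power figure for this comparison, so there is none to reproduce. The check is an enumeration, a rank count and an illustration.

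**Inputs.** Four contacts, 0 to 3; the bipolar rule (record on the complement); the monopolar rule (cathode 1 or 2, record on any two of the other three); sessions of about 45 minutes with 2-minute tremor trials or 10-minute bradykinesia trials. All are from Study Design and Procedures. Bipolar pairs are counted without regard to polarity.

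**1. Bipolar, same lead.**

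| Stimulate | Record |
|---|---|
| 0/1 | 2/3 |
| 0/2 | 1/3 |
| 0/3 | 1/2 |
| 1/2 | 0/3 |
| 1/3 | 0/2 |
| 2/3 | 0/1 |

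The map is one-to-one. Of 6 × 5 / 2 = 15 comparisons, 0 share a recording pair.

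**2. Would a recording-pair term help?** For an additive model, rank = stimulation levels + recording levels − number of unconnected blocks. In the bipolar table every row is its own block: 6 + 6 − 6 = 6, the same as with stimulation alone. No stimulation contrast (0 of 15) becomes estimable.

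**3. All eight same-lead configurations (six bipolar, two monopolar).** Of 8 × 7 / 2 = 28 comparisons, 7 could share a pair:
- monopolar 1- with 2-, on 0/3
- monopolar 1- with bipolar 1/2, on 0/3
- monopolar 2- with bipolar 1/2, on 0/3
- monopolar 1- with bipolar 0/1, on 2/3
- monopolar 1- with bipolar 1/3, on 0/2
- monopolar 2- with bipolar 0/2, on 1/3
- monopolar 2- with bipolar 2/3, on 0/1

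The other 28 − 7 = 21 cannot. With a fixed pair on a second lead, all 28 can.

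**4. Can geometry alone matter?** This is an illustration on assumptions not in the documents: one unit point source level with the mean position of the stimulating contacts, potential 1/r, lateral offset d in contact spacings. Signal = |1/r₁ − 1/r₂| over the two recording contacts. For monopolar 1- on 2/3 at d = 1: 1/√2 − 1/√5 = 0.707 − 0.447 = 0.260.

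| Stimulate, record | d = 0.5 | d = 1 | d = 2 |
|---|---|---|---|
| 1/2, 0/3 | 0.000 | 0.000 | 0.000 |
| 0/1, 2/3 | 0.240 | 0.183 | 0.088 |
| 0/2, 1/3 | 1.515 | 0.553 | 0.146 |
| 1-, 0/2 | 0.000 | 0.000 | 0.000 |
| 1-, 2/3 | 0.409 | 0.260 | 0.094 |
| 1-, 0/3 | 0.409 | 0.260 | 0.094 |
| 2-, 0/3 | 0.409 | 0.260 | 0.094 |

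Every row is a pairing that the protocol permits. Source strength is identical throughout, yet the reading runs from zero to clearly present. Monopolar 1- alone reads 0.000 or 0.260 at d = 1, depending on which permitted pair is used.

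**5. Trials available.** 45 / 2 = 22.5, so at most 22 tremor trials; 45 / 10 = 4.5, so at most 4 bradykinesia trials.

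**The case against.** A reader might infer that changing the stimulating contacts always changes the recording contacts, and so that no configuration effect on the DLEP can be interpreted. The documents do not support that. Seven of 28 same-lead comparisons can share a pair, a fixed second-lead pair covers all 28, reversing polarity within a bipolar pair leaves the recording pair unchanged, and nothing says that all six bipolar pairs will be used. What stands against this is that no section requires a common pair, and only some patients have a second lead.

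It may also be said that monopolar trials could bridge the bipolar ones in a model. If each monopolar setting were recorded on all three available pairs, the rank would be 8 + 6 − 2 = 12 and 21 of 28 contrasts would be estimable (all but the 7 involving bipolar 0/3). But the plan does not require those recordings. The model would also have to assume that moving the recording pair shifts the DLEP equally whichever contacts stimulate.

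A common pair is not a complete cure. On pair 0/3 the illustration gives 0.260 for monopolar 1- and 2- but 0.000 for bipolar 1/2 at d = 1, so that three-way comparison would repeat the problem. The zeros come from exact symmetry of one point source, and the model addresses amplitude only, not waveform. It shows that geometry can matter, not by how much in patients.

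One might add the changing reference and return to the charge. That is weak: Study Interventions describes differential recording between two DBS contacts, so a shared reference is largely common-mode. A different return alters the stimulating field, not the recording pair, and both locations are logged.

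Finally, the protocol bases its expected DLEP-symptom correlation on earlier work that varied stimulation intensity, which is safe within one montage. The comparison of the two recording systems, a stated specific aim, is outside this point.

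**Conclusion.** The point holds for same-lead bipolar recording. There the aliasing of stimulation configuration with recording pair is complete (0 of 15 comparisons separable) and follows from the protocol's own rule, with no modelling assumption. Randomized order, more subjects or an added recording-pair term within bipolar trials cannot undo it. In monopolar trials the mixing is possible rather than forced, because the choice of pair is left open. The DLEP-symptom correlation is affected only if trials are pooled across configurations, which the plan neither states nor rules out.

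Tremor and bradykinesia contrasts are untouched, and so are amplitude and frequency effects on the DLEP within one montage. It would be wrong to infer that the study's main correlation is invalid. The size of any distortion in practice is unknown; the 1/r figures are illustrative.

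**What to change.** 1. Log the recording pair for every trial. Estimate amplitude and frequency effects on the DLEP, and the DLEP-symptom correlation, within subject and within montage (same stimulating contacts and recording pair). A subject-by-montage blocking term does this and lets montages with few trials contribute, provided each has at least two.
2. Report same-lead configuration differences in the DLEP as effects of the stimulation-plus-recording combination, as the plan already does for signal-to-noise.
3. Draw stimulation-contact contrasts on the DLEP only where the recording pair is common: a fixed second-lead pair in dual-lead subjects, or monopolar 1- against 2- on pair 0/3, where the geometry is mirror-image. State that the distance from the stimulating contact to each individual recording contact still differs. Do not treat bipolar 1/2 on 0/3 as an equivalent comparison.

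The change is to analysis wording, one data item, and the choice of recording pair where the protocol leaves it open. The cost is fewer trials behind each DLEP comparison. With at most four bradykinesia trials, within-montage information is trials minus montages: 4 − 1 = 3 if all share one montage, 4 − 2 = 2 with two, and 4 − 4 = 0 if every trial differs. Stimulation artifact may also be larger on pair 0/3, which is not symmetric about contact 1 or contact 2.

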In subjects with tremor-dominant PD, we will record both the tremor and DLEP and/or LFP responses from the DBS electrode(s). Several trials will be conducted with different stimulation amplitudes, frequencies (≤ 185 Hz), temporal patterns, and contact configurations. The stimulation amplitude will be less than that identified to be uncomfortable to the subject or that generates side effects, as determined by a neurologist and/or neurosurgeon during the initial testing phase following implantation. The different stimulation parameters will be delivered in randomized order, and the subject will be blinded to the parameters. Measurements will be made during 2-minute trials, in which stimulation will be off for the first minute of the trial, and on for the remaining minute. At 30 s into both the off (baseline) and on phases of the trial, tremor will be measured for 20 s. The neural activity will also be measured from the electrode during both the off and on phases. The total amount of time necessary for data collection will be about 45 minutes.

Tremor will be measured using an accelerometer taped to the back of the subject's hand, and with the wrist extended such that the hand is parallel to the forearm. The elbow may either be supported or unsupported, depending on which induces greater tremor (determined prior to any trials in each subject). Tremor as measured by an accelerometer correlates well with clinical tremor rating scales [Elble et al, 2006].

In subjects with Parkinson's disease who do not have dominant tremor symptoms, we will record both bradykinesia testing responses and DLEP and/or LFP potentials. Several trials will be conducted with different stimulation amplitudes, mean frequencies (≤ 185 Hz), temporal patterns, and contact configurations. The maximum amplitude delivered will be determined as described as above. The different stimulation parameters will be delivered in randomized order, and the subject will be blinded to the parameters. Measurements will be made in 10-minute trials, in which stimulation will be off for the first five minutes of the trial, and on for the remaining five minutes. At approximately 90, 210 and 250 s into both the off (baseline) and on phases of the trial, bradykinesia will be measured for 20 s. The neural activity will also be measured from the electrode during both the off and on phases of the trial. The total amount of time necessary for data collection will be about 45 minutes.

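### The ANOVA lists no subject term and the symptom–DLEP correlations name no unit of analysis, although each subject gives several trials; fitted to all trials, the listed model has wrong standard errors.

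*Combined protocol and SAP*

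**What the plan says.** Study Design and Procedures sets up repeated trials in each subject: "Several trials will be conducted with different stimulation amplitudes", and also with different frequencies, temporal patterns and contact configurations. The order is randomised within the session: "The different stimulation parameters will be delivered in randomized order, and the subject will be blinded to the parameters". For tremor, "Measurements will be made during 2-minute trials"; for bradykinesia, "Measurements will be made in 10-minute trials". For either task, "The total amount of time necessary for data collection will be about 45 minutes". Each trial has its own off phase, which the plan calls baseline: "At 30 s into both the off (baseline) and on phases of the trial, tremor will be measured for 20 s". Bradykinesia is read three times in each phase. The amplitude ceiling is found for each subject from discomfort or side effects.

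Data Analysis and Statistical Considerations then gives the model: "We will perform ANOVA and post-hoc statistical analysis, in which the amplitude, frequency, and contact configuration used for stimulation will be the independent variables". The dependent variables are bradykinesia, tremor and DLEP measures. The next sentence reads: "We will also calculate correlation coefficients between tremor or bradykinesia and DLEP characteristics". Nothing in the document adds a subject or blocking term, a repeated-measures or mixed model, a per-subject analysis or a within-subject correlation. The stimulus-triggered averaging works across pulses; it is not said to reduce trials to one value per subject. The section does not say how symptom change is computed. It admits a subject with neural data in as few as one trial, so trial counts may be unequal.

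**The concern.** Trials from one subject share that subject's disease severity, electrode position and recording quality, so they are likely to resemble each other. A model whose only terms are the settings treats them as independent.

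This touches the main result. Purpose of the Study and Background and Significance aim at the relation between neural activity and change in symptoms, and they expect it to be strong. A coefficient over all trials combines two questions. One is whether subjects with larger DLEPs also respond more. The other is whether, in a given subject, a setting that evokes a larger DLEP also changes symptoms more. Choosing settings from the recorded signal rests on the second question. For the ANOVA, the risk is a real effect of a setting that is missed or, for amplitude, an effect declared too easily.

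**Working it through.** **No figure in the plan to reproduce.** The document gives no alpha, power, effect size or ICC. The maximum of 32 subjects rests on recruitment.

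**Trials per subject.** Tremor: 45/2 = 22.5, so at most 22. Bradykinesia: 45/10 = 4.5, so at most 4. Gaps between trials lower both. An equal split between the two recording systems would leave about 11 or 2 per system.

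**Assumptions.** Two-sided 5% test; 16 subjects on a task (the tremor/bradykinesia split is not given); normal data with total variance 1; ICC 0.1/0.3/0.5/0.7; 10,000 simulated data sets per cell unless stated.

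**1. One two-level setting balanced within subject, 4 trials.** The subject effect cancels from the contrast, so its true standard error is proportional to √(1−ICC). The model without subject uses the total SD. Its standard error is therefore too large by about 1/√(1−ICC), which at ICC 0.5 is 1/√0.5 = 1.41.

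| ICC | 0.1 | 0.3 | 0.5 | 0.7 |
|---|---|---|---|---|
| SE ratio, simulated | 1.06 | 1.20 | 1.41 | 1.81 |
| Null rejection without subject | 4.0% | 2.2% | 0.8% | 0.2% |
| Power, 0.4 SD effect, without subject | 34% | 33% | 31% | 28% |
| Power, with subject | 37% | 46% | 60% | 82% |

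**2. Amplitude, null rejection without subject.** The ceilings (arbitrary units) and fractions are assumed. The ranges run over ICC 0.1 to 0.7.

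| Ceiling; fractions used | 4 trials | 22 trials |
|---|---|---|
| 3–5; 25–100% | 4.3% down to 1.1% | 7.4% to 19.7% |
| 2–5; 25–100% | 4.9% down to 4.2% | 10.9% to 38.2% |
| 1.5–6; 50–100% | 6.7% to 18.4% | 20.6% to 57.8% |

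The span is about 1–18% with 4 trials and 7–58% with 22.

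**3. All-trials correlation, no association.** With m trials per subject, the variance of r is inflated by about 1 + (m−1)·ICCx·ICCy. At ICC 0.5 in both variables:
- m = 4: 1 + 3 × 0.25 = 1.75; 1.96/√1.75 = 1.48; two-sided rejection 13.8%.
- m = 22: 1 + 21 × 0.25 = 6.25; 1.96/2.5 = 0.784; two-sided rejection 43.3%.

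| Equal ICC in both | 0.1 | 0.3 | 0.5 | 0.7 |
|---|---|---|---|---|
| 4 trials, simulated | 5.3% | 8.3% | 13.7% | 21.7% |
| 10 trials | 6.3% | 14.6% | 27.7% | 40.3% |
| 22 trials (upper bound) | 7.1% | 24.1% | 42.6% | 56.6% |

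With 32 subjects (4,000 runs) the rates at ICC 0.5 are 14% and 43% for 4 and 22 trials, so the number of subjects hardly matters. The within-subject correlation rejects in 4.7–5.4% of runs in every cell.

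An on-minus-off change may have a low ICC: R/(R+2e), where R is the between-subject variance in response and e the noise variance. With e = 0.5 and R = 0/0.1/0.2, this is 0/0.09/0.17. With DLEP ICC 0.5 and change ICC 0/0.1/0.17, the rate is 5/7/8% (4 trials), 5/10/13% (10) and 5/16/22% (22).

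**4. Value of the all-trials coefficient.** With equal ICCs it is about ICC·r_between + (1−ICC)·r_within. Take r_within = −0.6 and ICC 0.3/0.5/0.7. The simulations use 10 trials.
- r_between = 0: formula −0.42/−0.30/−0.18; simulated −0.43/−0.32/−0.20.
- r_between = −0.6: formula −0.60 throughout; simulated −0.60/−0.60/−0.59.
- r_between = −0.8: formula −0.66/−0.70/−0.74; simulated −0.65/−0.69/−0.74.

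**The case against.** The strongest reply is that the text is silent rather than wrong. A short protocol may list the manipulated variables and leave the repeated-measures structure to the study statistician, and a per-subject or mixed analysis would fit the wording. A reader might infer that the plan pools trials; the document does not say so. What remains is that the listed model, run on the planned data, has no subject term, and nothing elsewhere supplies one.

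Second, the plan only says that coefficients will be calculated. It gives no alpha and no decision rule, so the false-positive rates apply only if the coefficient is tested. That is right. The mixing of two relations in the coefficient does not depend on a test.

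Third, each trial carries its own off phase, and the stated aim is symptom change. With change scores of low ICC and 4 trials, the rates are 5–8%, close to nominal. This stands for the bradykinesia task, but the plan does not state that change scores will be used.

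Three stronger readings are not supported. Pooling does not raise false positives everywhere: for a balanced setting it lowers them. It does not always weaken a real within-subject relation: the third and fourth parts of the simulated coefficients show it unchanged or strengthened when the between-subject relation has the same sign. Nor does amplitude always fall between a balanced setting and the correlation: at ICC 0.1 with 22 trials and the widest ceilings it rejects in about 21%, against 7% for the correlation.

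**Conclusion.** The point holds as a gap in specification with real consequences, and it should be fixed before analysis. Fitted to all trials, the listed ANOVA gives standard errors that are too large for a setting balanced within subject, and possibly too small for amplitude. An all-trials correlation does not answer the stated question, because the same within-subject relation can appear as anything from −0.20 to −0.74 in the cases worked through.

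The sizes rest on assumed ICCs, an assumed 5% level, 16 subjects per task and, for amplitude, assumed ceilings; the document gives none of these. Twenty-two trials is an upper bound. It would be tempting to read the rise from 31% to 60% power as the gain to expect. That figure is for one balanced two-level factor. Four bradykinesia trials cannot balance amplitude, frequency, contact configuration and temporal pattern within a subject, so the gain does not carry over in full.

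**What to change.** Add one paragraph to Data Analysis and Statistical Considerations:
- State the unit of analysis: the trial, nested in subject. Average or nest the three bradykinesia readings in a phase, so that they are not counted as separate trials.
- Add subject to the ANOVA, as a mixed model with a random subject intercept. Let setting effects vary by subject where this can be estimated. If they vary with SD 0.4 at ICC 0.5, an intercept alone rejects in 6.6% (4 trials) to 21.5% (22 trials) under the null.
- Define symptom change from the off phase of the same trial (on minus off, or off as covariate). DLEP has no off value, because stimulation pulses evoke it.
- Report a within-subject (repeated-measures) correlation between DLEP and symptom change, and show any between-subject correlation separately. Subjects with two or more trials contribute to the within-subject coefficient.
- As a check, apply a t-test to the subjects' Fisher-z correlations, using subjects with more than 3 trials, since the Fisher-z variance is 1/(m−3). It holds about 5% when the correlation varies between subjects. In that case the repeated-measures p-value can reach 12% (4 trials) or 34% (22 trials), with an SD of 0.4.

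The cost is a paragraph and a few lines of code; no new data are needed. Some p-values will become less favourable. The check loses power with few trials: at r = −0.4, ICC 0.5, 16 subjects and 4 trials it has 63%, against 83% for the repeated-measures correlation. With about 4 bradykinesia trials spread over several settings, random slopes will not be estimable, and the paragraph should say that those results rest on a random intercept. If trials are split by recording system, about 2 bradykinesia trials per system remain and the check is not available there.

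### Temporal pattern is varied but missing from the ANOVA factors, and LFPs are missing from the ANOVA outcomes and the symptom correlation

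*Combined protocol and SAP*

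**What the plan says.** **Stimulation factors.** Study Design and Procedures describes the trials for each symptom group. For subjects without dominant tremor: "Several trials will be conducted with different stimulation amplitudes, mean frequencies" (up to 185 Hz), then "temporal patterns, and contact configurations". The tremor-dominant group has the same four factors, with frequency not qualified as a mean. Data Analysis and Statistical Considerations gives the model: "the amplitude, frequency, and contact configuration used for stimulation will be the independent variables, and with dependent variables describing bradykinesia, tremor, and DLEP characteristics". It lists three stimulation factors and does not mention temporal pattern.

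**Neural signals.** Purpose of the Study names two kinds of neural activity to be recorded, DLEPs and LFPs. It sets out to measure how stimulation affects neural activity and to correlate neural activity with symptoms. Background and Significance treats the two signals jointly as a candidate biomarker, to be tested first in the operating room. In the analysis section the outcomes are those quoted above, and the correlation is: "We will also calculate correlation coefficients between tremor or bradykinesia and DLEP characteristics". LFPs appear in that section in three other places:
- the data description: "The data set will consist of recordings of neural and/or LFP recordings"
- the blinded localisation exercise: "Other study staff will analyze DLEP and/or LFP recordings obtained during surgery to generate a prediction of recording contact location"
- the rule for entering the analysis: "DLEP and/or LFP data are observed during at least one trial"

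**The concern.** Two things that the study sets out to do are not carried into its main analyses.

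First, a factor that is deliberately varied has no term in the model. Fitting the stated ANOVA to all the trials gives no estimate of the pattern effect. If pattern matters, its effect adds to residual variation. If certain patterns tend to be run at certain frequencies, part of it is credited to frequency. Where frequency is a mean frequency, two trains with equal means and different patterns carry the same frequency code. Randomising the order of settings does not help: it balances time order, not which patterns are paired with which frequencies.

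Second, the LFP part of the stated purpose has no planned test of stimulation effect and no planned correlation with symptoms. A later LFP result of either kind would rest on features and tests chosen after the data were seen.

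**Working it through.** **1. Setting the sections side by side.**

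| | Study Design / Purpose | ANOVA | Symptom correlation |
|---|---|---|---|
| Stimulation factors | 4: amplitude, frequency, temporal pattern, contact configuration | 3: pattern absent | not applicable |
| Neural signals | 2: DLEP, LFP | 1: DLEP | 1: DLEP |

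Pattern cannot be read as part of frequency, because the design section lists them separately. DLEP is unlikely to be shorthand for both signals, because the same analysis section names both when it means both (localisation and inclusion rule).

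**2. Trials available.** A session lasts about 45 minutes. Bradykinesia trials take 10 minutes: floor(45/10) = 4. Tremor trials take 2 minutes: floor(45/2) = 22. These are ceilings, with no allowance for set-up or for switching between the two recording systems. At an assumed two levels per factor, the present three factors already make 2 × 2 × 2 = 8 cells, and a four-factor main-effects model has 1 + 4 = 5 parameters. Four bradykinesia trials in one subject cannot support either, so any model must pool subjects.

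**3. Loss if pattern and frequency are unrelated.** Let the pattern effect be d within-subject SDs, with half the trials patterned. The omitted term adds variance d²/4, so the residual SD becomes √(1 + 0.25d²):
- d = 0.25: 1.008
- d = 0.5: √1.0625 = 1.031, about 3% wider standard errors
- d = 1.0: 1.118

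**4. Error if they are related.** The documents give no settings grid, effect size, group split or significance level, so everything here is assumed: 16 subjects in a symptom group (half of the maximum 32), d = 0.5, no true frequency effect, four frequency levels, half the trials patterned, a fixed subject effect, F test at 5%. Three grids were simulated: the same four levels for patterned and regular trains (unrelated), levels 1–3 against 2–4 (partial overlap), and levels 1–2 against 3–4 (none shared). Trial totals:
- 16 × 2 = 32: bradykinesia, each setting run on both recording systems
- 16 × 4 = 64: bradykinesia, each setting run once
- 16 × 11 = 176: tremor, each setting run on both systems (22/2 = 11)

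Frequency wrongly flagged when pattern is omitted (ranges span repeated runs):

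| Trials | Unrelated | Partial overlap | None shared |
|---|---|---|---|
| 32 | 5–6% | 8–10% | 14–16% |
| 64 | 5–6% | 13–15% | 33–34% |
| 176 | 4–5% | 32–33% | 78–79% |

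Under partial overlap, d = 0.25 / 0.5 / 1.0 gives 7% / 15% / 40% with 64 trials and 11% / 33% / 87% with 176. Also fitting amplitude and contact configuration, at an assumed three levels each, gives about 7% with 32 trials and 13% with 64 (partial overlap, d = 0.5).

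**5. With pattern added.** In the two grids with shared levels the frequency error rate returns to about 5–6%. Under partial overlap the frequency standard error is on average 1.12 times wider with 64 trials and 1.10 times with 176 (1.00 to 1.30 by contrast). Power to detect the 0.5 SD pattern effect is 0.46 (unrelated) and 0.31 (partial) with 64 trials, and 0.90 and 0.75 with 176. With no shared level, pattern is completely aliased with frequency and adding the factor recovers nothing.

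**6. LFP.** The count of LFP variables in the ANOVA outcomes and the correlation is zero. The number of subjects with LFP data only is unknown.

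**The case against.** The best reply on pattern is that the plan never says patterned trials enter the three-factor ANOVA. They might be set aside and analysed on their own, which is one of the remedies below. That stands: the defect is that their handling is unstated, and the consequences in steps 3 and 4 are conditional on their being included. No hypothesis about pattern is stated either.

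The rates also rest on an invented grid and effect size. A reader might infer from the table that the frequency result will be wrong a third or more of the time. The documents do not support that. The largest figures need a grid with no shared frequency level, which the plan does not describe and which adding a factor could not repair. They therefore do not measure the harm from the missing factor. The mean-frequency wording applies only to the bradykinesia group, where trials are fewest and the rates lowest. The study has no primary endpoint or stated significance level, so a false-positive rate is a yardstick of bias and not a decision rule in the plan.

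On LFPs, a reader might infer that they have no planned analysis. That is wrong: they feed the blinded prediction of contact location, in line with the expectation in Background and Significance that signals vary with electrode placement. The specific symptom expectation in that section names DLEP alone, and LFP recording is optional in much of the protocol. What remains is the mismatch with the general purpose and biomarker statements. Nor does an LFP-only subject contribute nothing: the symptom ANOVA and the localisation exercise still use that subject's data. Finally, DLEP characteristics are not defined in advance either, so the risk of choosing features after the fact is not peculiar to LFPs.

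**Conclusion.** Both omissions stand on the text and do not depend on the simulation. As written, the ANOVA leaves out a factor that the design varies and does not say what happens to patterned trials. If all trials are included, pattern is not estimated. The cost is then small if pattern and frequency are unrelated (about 3% wider standard errors at 0.5 SD). If they partly overlap it is a bias towards a false frequency effect, illustrated by about 10% wrong flags with 32 trials, 13–15% with 64 and 32–33% with 176. Those figures hold only under the assumptions in step 4, and the actual bias cannot be determined without the settings used.

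The LFP part of the purpose has no planned stimulation-effect or symptom analysis, and an LFP-only subject adds symptom data but no neural variable to the ANOVA and the correlation. This should be corrected before analysis because the remedy is cheap. It does not undermine the study as a whole.

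**What to change.** 1. State how patterned trials are handled. Where patterned and regular trains share frequency levels, add temporal pattern as an ANOVA factor, pooling subjects with a subject effect. Where they share none, analyse patterned trials separately or descriptively and keep them out of the frequency comparison.
2. Define one or a few LFP features in advance, for example power in a stated spectral window, on phase and change from off phase. Say how stimulation artifact is dealt with in on-phase measures. Add these features as ANOVA outcomes and compute the same symptom correlation as for DLEP.

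Both additions may be labelled exploratory.

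**Cost.** A short paragraph and no new data, since the design already provides that "The neural activity will also be measured from the electrode during both the off and on phases". There will be a few more tests, and the frequency standard error will be about 1.1 times wider under partial overlap. Where no level is shared, a frequency comparison on regular trains alone keeps the error rate near 5%, but with half the trials and only two of the four assumed frequencies. No wording recovers a pattern effect in that case.
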